11.2. Safety Assessments

11.2.1. Adverse Events

Adverse events will be collected for each subject. Subjects should be queried in a non-leading manner, without specific prompting (eg, "Has there been any change in your health status since your last visit?"). See Section 12, Safety Reporting.

AEs will be monitored throughout the study at all visits including telephone, text, or email assessments.

Information on AEs carried over from the core-study will be described in the DMP.

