11.5.3. Withdrawal Period

All subjects, including those who complete treatment and those who discontinue treatment, will complete weekly in-clinic visits during the 3 week study medication withdrawal period. In addition to the weekly visits, the CSSA and DESS will be completed during the 3 week study medication withdrawal period on non-clinic visit days. Clinical site staff will call the subject every other day during the study medication withdrawal period, beginning the second day after the last dose of study drug, unless a clinic visit is scheduled for that day (up to 3 times per day if the clinical site staff are unable to contact the subject on the first 2 attempts). Clinical site staff will record the responses to the CSSA and DESS in the subject's source information and in the CRF with the contact date and time. During these calls, clinical site staff will also record AE(s) and concomitant medications.

A window of ± 1 day will be allowed for each weekly clinic visit and telephone call. If the subject cannot be contacted on a given day, during the next contact the study site staff will

retrospectively collect the missed CSSA and DESS, in addition to the current day's CSSA and DESS, as necessary.

11.5.3.1. Visit 16E (Week 53; Day 371 ± 1^5) and Visit 17E (Week 54; Day 378 ± 1^6)

The following study related procedures will be performed:

- Record concomitant medications
- Collect vital signs and weight
- Perform ECG
- Record AEs
- Administer Scales: MADRS, C-SSRS, BE-CGI-S, HAM-A, CSSA, and DESS

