7.4.2. Adverse Events

All AEs are coded using Medical Dictionary for Regulatory Activities (MedDRA) version 19.0 or higher.

Treatment-Emergent Adverse Event (TEAE)

Treatment-emergent adverse events (TEAEs) are those reported adverse events with onset data on or after the first day of the open-label treatment period through 7 days after study drug discontinuation (14 days for serious adverse events and deaths). The start of the open-label treatment period is defined as Day 1 for subjects previously randomized to placebo group and the OL Baseline visit date for subjects previously randomized to dasotraline groups.

AEs with a start date prior to the first day of the OL treatment period which are reported to have an increase in intensity, or which are reported to have a attribution in relationship to study medication (ie, attribution to possible related, probably related, related) after the first day of the OL treatment period are considered as TEAEs.

Discontinuation-emergent adverse events (DEAEs) are defined as AEs which have an onset after the last dose date of study drug through the Week 55 visit (ie, the last study visit in the withdrawal period).

Table summary of AEs will be limited to TEAEs and DEAEs. All AE data will be displayed in data listings. For the sake of simplicity, hereafter TEAE is referred to as AE.

The overall incidence (ie, number and percent of subjects with one or more AE in each category) of AEs, serious AEs, deaths, AEs leading to discontinuation, study drug-related AEs, study drug-related AEs leading to discontinuation, serious AEs leading to discontinuation, and serious

study drug-related AEs, and serious study drug-related AEs leading to discontinuation will be summarized by analysis group.

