Each AE will be classified as ‘related’, ‘not related’, and ‘not specified’. TEAEs with a missing AE relationship will be classified as ‘not specified’. AE summary by the relationship to the study medication will be based on the highest relationship within an SOC and PT. Response values will be ranked in order from minimum to maximum as ‘not specified’ < ‘not related’ < ‘related’.

AE maximum severity

322

AEs with a missing severity will be classified as ‘not specified’. AE summary by the severity will be based on the maximum severity within an SOC and PT. Response severity values will be ranked in order from minimum to maximum as ‘not specified’ < ‘mild’ < ‘moderate’ < ‘severe’.

AE maximum action taken

AEs with a missing action taken will be classified as ‘unknown’. AE summary by the action taken will be based on the maximum action taken within an SOC and PT. Response action values will be ranked in order from minimum to maximum as ‘not applicable’ < ‘unknown’ < ‘dose increased’ < ‘unchanged’ < ‘dose reduced’ < ‘drug interrupted’ < ‘drug withdrawn’.

AE maximum outcome

AEs with a missing outcome will be classified as ‘unknown’. AE summary by the outcome will be based on the maximum outcome within an SOC and PT. Response outcome values will be ranked in order from minimum to maximum as ‘unknown’ < ‘recovered/resolved’ < ‘recovered/resolved with sequelae’ < ‘recovering/resolving’ < ‘not recovered/not resolved’ < ‘fatal’.

AEs of Special Interest (AESI)

A list of preferred terms that are to be combined for assessment of each of pre-specified adverse events category as below are provided in [Attachment 9.3](#).

- cardiovascular-related AEs
 - Cardiac arrhythmias
 - Vital signs-related
- metabolic-related AEs
 - Weight-related
 - Metabolic-Related (excluding weight)
- Neuropsychiatric-related AEs,
 - Neuropsychiatric AEs
 - Psychosis or Mania
 - Psychosis
 - Mania
- Combined insomnia
- Suicide and self-injury related AEs
- Spontaneous abortion /miscarriage (for female subjects only).
- Drug abuse and dependence (for AEs onset on/prior to the last study dose)
- Potential drug abuse (for AEs onset on/prior to the last study dose)
- Drug withdrawal related AEs (for AEs onset after the last study dose)

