Definition of above AESI categories were initially provided in the integrated statistical analysis plan (ISAP) of the Integrated Summary of Safety (ISS) of Dasotraline BED NDA (NDA number: 213025). For final analysis of study SEP360-322, definitions of AESIs, including cardiac

322

arrhythmias, combined insomnia, psychosis, mania, suicide and self-injury, spontaneous abortion /miscarriage, drug abuse and dependence, drug withdrawal, and potential drug abuse, are exactly same as what were defined in the ISAP, since their definitions are either directly based on standard SMQs or from other standard terms.

For other AESI categories, including vital signs-related AEs, weight-related AEs, metabolic-related (excluding weight) related AEs, and neuropsychiatric AEs, their AE preferred terms are determined and verified by medical review of coded AE terms during data review and finalized prior to the final database lock. Definitions of these AESIs were obtained per medical review from the accumulative database of dasotraline clinical program. Since more data are obtained from study SEP360-322 after the BED NDA submission, additional AE preferred terms might be identified and added to preferred lists of definition. AE preferred terms that had been already identified in ISS ISAP of BED NDA will be kept as they are.

Except of category of drug withdrawal related AEs, the incidence of TEAEs with special interest by AESI category and PT will be summarized by analysis group, by severity, by the action taken regarding the study medication, as well as by the outcome based on the safety population. For “Spontaneous abortion /miscarriage” related AEs, the incidence will be calculated based on the number of female subjects in each analysis group as denominator.

Listings will also be generated for deaths, SAEs, AESI, and discontinuations due to AEs. All adverse events regardless of treatment emergent status will be provided in the AE data listing.

AEs by Exposure

The TEAEs will be summarized by exposure to study drug using time intervals beginning with the earliest concurrent exposure to study drug for following AE summary as needed. Denominators for exposure intervals will be based on the number of subjects who were exposed as of the first day of the interval; for cases where events meet the treatment-emergent definition but start after the last dose, the exposure interval for the event will be considered the interval of the last day of exposure to study medication.

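### The TEAE tables, including those by exposure interval, mix on-drug onsets with onsets in the first 7 days off drug (14 if serious), when scheduled contact is about 8 times denser

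*SAP*

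**What the plan says.** Three rules in SAP 7.4.2 act together.

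- **TEAE.** The window runs from the start of the open-label period "through 7 days after study drug discontinuation (14 days for serious adverse events and deaths". Protocol 15.3.3.1 has the same window.
- **DEAE.** These are "AEs which have an onset after the last dose date of study drug through the Week 55 visit". A non-serious AE starting on Days 1 to 7 off drug, or a serious one on Days 1 to 14, meets both definitions.
- **AEs by Exposure.** The rule is that "for cases where events meet the treatment-emergent definition but start after the last dose, the exposure interval for the event will be considered" the one that holds the subject's last day on drug. The denominator is the number of subjects still on drug when the interval opens. The intervals are Days 1-13, 14-27, 28-83, 84-167 and 168 onward, the last without an upper limit.

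The way AEs are found changes at the last dose. On treatment they are collected at clinic visits and, after Week 4, at one contact midway between 4-weekly visits (Protocol 7.1, 11.5.2). Off drug, sites telephone every other day from the second day and see the subject weekly (Protocol 11.5.3). They complete the 18-item CSSA and the 43-item DESS at these contacts, and "During these calls, clinical site staff will also record AE(s) and concomitant medications". SAP 7.4.1 confirms that neither scale is used before Week 52/EOT. The general instruction for AEs is an open question: "Subjects should be queried in a non-leading manner, without specific prompting".

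**The concern.** The primary objective is long-term safety on dasotraline. A reader of the by-exposure tables will take an event in the last interval as one that arose after about six months on drug. Under the plan, some of those events will have started after the drug was stopped, in a week with far more opportunity to report them. The CSSA covers mood, anxiety, irritability, sleep, paranoia and suicidality (Protocol 11.2.6.2). These overlap the insomnia, neuropsychiatric and suicide-related AESI categories, which carry no onset limit, and AESIs are among the by-exposure tables.

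The SAP separates onsets at the last dose in some places and not in others. One AESI category is headed "Potential drug abuse (for AEs onset on/prior to the last study dose"), and the withdrawal category takes only later onsets. The insomnia Kaplan-Meier plot censors at the last dose subjects who have had no insomnia by then. A first insomnia on Day 3 off drug would thus be censored in that plot but counted in the by-exposure table. The SAP does not say why the rules differ.

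**Working it through.** The documents state no figure for contact density or for AE rates by interval, so there is nothing to reproduce. The steps are a count of contacts, the mechanics of the rule, and an illustration of size.

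**1. Contact density.** On drug there is one scheduled contact per 14 days, or 0.5 per week. In the first week off drug there are calls on Days 2, 4 and 6 and a clinic visit on Day 7: 4 per week. Ratio: 4 / 0.5 = 8. The visit windows and the handling of the EOT visit move this between 3 / 0.5 = 6 and 5 / 0.5 = 10.

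**2. What the rule does to each interval.** It adds off-drug onsets to the numerator and nothing to the denominator, so a percentage can only rise or stay the same. Every subject counted from Day 168 takes the last dose in that interval, so all of them can contribute an off-drug week. In earlier intervals only those who stop there can. The relative effect depends also on interval length. The last column is length / 197: the share of subjects who must stop in an interval for its relative gain in time to equal that of the last one.

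| Interval (days) | Length | Scheduled contacts | 7 off-drug days / length | Break-even share stopping |
|---|---|---|---|---|
| 1-13 | 13 | 0 | 53.8% | 6.6% |
| 14-27 | 14 | 1 | 50.0% | 7.1% |
| 28-83 | 56 | 4 | 12.5% | 28.4% |
| 84-167 | 84 | 6 | 8.3% | 42.6% |
| 168-364 | 197 | 15 | 3.6% | 100% |

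In the last interval the off-drug week adds 4 contacts to 15, or 27%.

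**3. Illustrative size.** None of these inputs is in the documents: constant dropout of 20% to 60% over 52 weeks; 52-week incidence I of 5% or 50%; off-drug reporting hazard m = 1, 2 or 8 times the on-drug hazard h = -ln(1 - I)/364; every subject followed for 7 days off drug. In the last interval:

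added share = (share event-free in the interval) x (1 - exp(-7hm)).

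For I = 50% and 40% dropout, h = 0.001904 per day, and 27.6% have an on-drug event in the interval, so 72.4% are event-free:

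- m = 1: 0.724 x 0.0132 = 1.0 point, giving 28.5%
- m = 2: 0.724 x 0.0263 = 1.9 points, giving 29.5%
- m = 8: 0.724 x 0.1011 = 7.3 points, giving 34.9%

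Over all the dropout rates:

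| Assumed 52-week incidence | Added from Day 168, m = 1 / 2 / 8 (points) | Added in earlier intervals, all m (points) |
|---|---|---|
| 5% | 0.1 / 0.2 / 0.8 | 0.0 to 0.15 |
| 50% | 0.9-1.0 / 1.9-2.0 / 7.1-7.6 | 0.0 to 1.8 |

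In relative terms the last interval rises by 3% to 36% and earlier ones by 0.4% to 14%. With constant dropout only 1% to 19% of subjects stop in any one earlier interval, always below that interval's break-even share. Front-loaded dropout could exceed it.

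**4. Drug remaining off treatment.** With the half-lives in Protocol 4.2 (47.1 to 77.0 hours) and simple exponential decay, the fraction left at Day 7 is 0.5^(168/47.1) = 8% to 0.5^(168/77.0) = 22%. The average over the seven days is (1 - 0.084)/(3.567 x ln 2) = 37% to (1 - 0.220)/(2.182 x ln 2) = 52%.

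**The case against.** The case for leaving the plan alone has real strength.

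- **A TEAE window after the last dose is defensible.** On average 37% to 52% of the drug is still present over that week, and the window is in the protocol. This stands, and the window should stay.
- **Contact density is not AE yield.** On-drug questions cover the whole time since the last contact, so eight times the contacts need not mean eight times the AEs. The open-question instruction is not confined to the treatment period, and no text says that CSSA or DESS items are transcribed as AEs. Prompting by the scales is plausible but inferred.
- **Not everyone contributes an off-drug week.** SAP 6.1.8 provides for subjects who never enter the withdrawal period.
- **Raw percentages across these intervals cannot show late emergence anyway.** The last interval is 2.3 to 15 times longer than the others.
- **The tables are optional and descriptive.**

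A reader might infer that neither set of tables separates on-drug from withdrawal events. That is not so: DEAEs are by definition off-drug onsets, and SAP 7.4.2 tabulates them for Days 1-7, 8-14 and 15 onward. A reader might also suppose that if 10% or 20% of subjects report a new AE in the first week off drug, the last interval rises by 10 or 20 points. That restates an assumption as a result. It is also an upper limit, because subjects already counted in that interval add nothing.

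What remains is narrower: the TEAE tables combine two kinds of onset, found with different intensity, and do not show how many of each they hold.

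**Conclusion.** The point holds as a matter of presentation on the TEAE side. The double classification, the placement in the last on-drug interval, the unchanged denominator and the roughly 8-fold rise in scheduled contact all follow from the documents. So does the direction: the rule cannot lower an interval percentage.

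The size does not follow, because the documents give no off-drug AE rate and no dropout pattern. The illustration gives 0.1 to 7.6 points from Day 168 and 0.0 to 1.8 earlier. The high end needs a 50% incidence and an off-drug hazard 8 times the on-drug one; at 5% incidence, closer to an individual preferred term, the addition is at most 0.8 points. These are scenario values, not bounds. That the last interval gains most in absolute points assumes similar off-drug reporting, and similar shares still event-free, in all intervals. The documents do not support the stronger reading that the rule must create a false pattern of late-emerging AEs: if more than about 7% of subjects stop in each of the first two intervals, those intervals are inflated more in relative terms.

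**What to change.** In SAP 7.4.2, keep the 7/14-day TEAE window and change the display.

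1. **AEs by Exposure.** Count only onsets on or before the last dose in the exposure intervals. Replace the sentence that assigns later onsets to the last on-drug interval with a separate row or column for TEAEs that start after the last dose. It must include SAEs and deaths up to 14 days. Simply deleting post-dose onsets would remove those events from the by-exposure tables of serious AEs and of AEs leading to discontinuation.
2. **Overall TEAE, AESI and SOC/PT tables.** Add the same split: 'onset on or before last dose' and 'onset after last dose (also reported as DEAE)'.

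The cost is one derived flag and one extra column. The downside is that events in the first days off drug, while much of the drug remains, are shown apart from the on-drug intervals. No event leaves the report, and the protocol's TEAE definition is unchanged.

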5. STUDY OBJECTIVES

5.1. **Primary Objectives**

The primary objective of the study is to evaluate the long-term safety and tolerability of flexiblydosed dasotraline (4, 6, or 8 mg/day) in adults with binge-eating disorder (BED) who have completed a prior dasotraline study in BED by:

- The incidence of AEs, discontinuations due to AEs, and serious AEs (SAEs)
- The frequency and severity of suicidal ideation and suicidal behavior using the Columbia Suicide Severity Rating Scale (C-SSRS)
- Changes in 12-lead electrocardiograms (ECGs), vital signs, body weight, body mass index (BMI), and clinical laboratory results

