6.1.8. Analysis Populations

The Safety Population: All subjects who receive at least one dose of study medication. The safety population mainly is used for the data analyses of the safety data collected through Week 52 or during the open-label treatment period.

The Withdrawal Population: The withdrawal population includes all subjects who receive at least one dose of study medication, and either early terminate from the study drug during the OL treatment period or complete the 52-week OL treatment period, and have at least 1 assessment after the last study drug for any evaluation. The withdrawal population is used to summarize the safety and effectiveness assessments collected in the withdrawal period. Withdrawal analysis will be presented by analysis group.

The ‘Modified’ Withdrawal Population: all subjects in the withdrawal population plus the subjects who either are early terminated during the OL treatment period or complete the 52-week OL treatment period and do not enter the withdrawal period, but the last study dose dates are at least 2 days prior to their last study visit. The modified withdrawal population will be only used for summary of adverse event data which could be retrospectively collected.

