The AEs also will be summarized by system organ class (SOC) and preferred term (PT) by presenting the number and percentage of subjects with each AE category. The incidence of AEs (by preferred term, grouped by SOC, and presented by analysis group) will also be summarized by severity, by the relationship to study medication, by the action taken regarding the study medication, as well as by the outcome. If a subject has the same AE on multiple occasions, the highest severity (severe, moderate, mild) recorded for the event and the highest drug relationship (unrelated, unlikely to be related, possibly related, probably related, and definitely related) will be presented, respectively. The relationship to study medication will be presented by 2 categories: related (which includes possibly related, probably related, and related, as determined by investigators), and not related (which includes unrelated and unlikely to be related, as determined by investigators). Furthermore, for AE summary by SOC and PT or by PT only, the following combined preferred terms will be summarized as well:

- Insomnia: Insomnia, Initial insomnia, Middle insomnia, Terminal insomnia
- Hallucination: Hallucination; Hallucination, auditory; Hallucination, gustatory; Hallucination, olfactory; Hallucination, synaesthetic; Hallucination, tactile; Hallucination, visual; Hallucinations, mixed; Hypnagogic hallucination; Hypnopompic hallucination; Somatic hallucination.

A Kaplan-Meier plot of the time to the first onset of treatment emergent insomnia (combined term) during the extension study will be presented by analysis group. Time to the first onset (in days) is defined as the earliest onset date of insomnia – start date of OL treatment period + 1. Subjects who do not experience any insomnia on or before the last dose date will be censored on the day of last dose.

Prevalence rate of insomnia (combined term) at a study day in the open-label treatment period is defined as number of subjects experiencing insomnia on the day divided by number of subjects remaining on open-label study treatment period at that time point. It is notable that subjects may experience multiple insomnia episodes during the study. Prevalence rate over time will be summarized and presented graphically by analysis group.

AE maximum relationship

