- AEs by SOC and PT, Serious AEs by SOC and PT, and AEs leading to discontinuation by SOC and PT (sorted alphabetically by SOC and PT within SOC).
- AEs by PT, AEs with special interest by PT (sorted by descending order per frequency count)

Exposure categories to be summarized are given below:

- Exposure categories : 1-13 days, 14-27 days, 28-83 days, 84-167 days, \geq 168 days.

AEs by Subgroup

The TEAEs will be summarized by SOC, PT for subgroups (see [Section 6.1.12](#)) below:

322

- Age group at OL Baseline (years): < 40 years, ≥ 40 years
- Gender: Male, Female
- Race: White, Non-white
- BMI at OL Baseline: Non-obese , Obese class I/II, Obese class III

Discontinuation-Emergent Adverse Event (DEAE) (ie, AEs Onset After Last Study Dose)

All summary of DEAEs will be based on a ‘modified’ withdrawal population (see [Section 6.1.8](#)), which includes all subjects in the withdrawal population plus the subjects who do not enter withdrawal period, but their last study dose dates are at least 2 days earlier than their last study visit (ie, Week 52/EOT visit). The rationale of defining ‘modified’ withdrawal population is that the AE information after the last study dose is expected to be continuously collected till the last study visit

The overall incidence of DEAEs and serious DEAEs will be summarized by analysis group. The DEAEs also will be summarized by SOC and PT, and by PT of each analysis group.

In addition, incidence of DEAEs by SOC and PT will be also summarized using time intervals beginning with the earliest AE concurrent withdrawal duration in the withdrawal period, where denominators in percentage calculation for withdrawal duration intervals (in days) will be based on the number of subjects whose withdrawal duration are no less than the first day of the interval. Withdrawal duration (in days) will be derived as the last withdrawal visit date minus the last dose date +1 and withdrawal duration categories to be assessed are 1-7 days, 8-14 days, and ≥ 15 days.

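### Adverse event (AE) percentages carry no person-time: the by-exposure intervals run from 13 to about 197 days, so they rise with interval length alone, and crude overall incidence falls with dropout

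*SAP*

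**What the plan says.** The primary objective in Protocol 5.1 is "to evaluate the long-term safety and tolerability of" flexibly dosed dasotraline. Planned treatment is 52 weeks: SAP 6.1.8 refers to subjects who "complete the 52-week OL treatment period", and the Week 52 visit is at Day 364 ± 1.

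For overall AEs, SAP 7.4.2 gives "The overall incidence (ie, number and percent of subjects with one or more AE in each category". The tables by system organ class and preferred term, and those for AEs of special interest (AESIs), are also counts and percentages of subjects. No person-time rate for AEs appears in the SAP text supplied.

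The same section plans AE tables by exposure, "for following AE summary as needed", covering AEs, serious AEs (SAEs), AEs leading to discontinuation and AESIs. The intervals are "1-13 days, 14-27 days, 28-83 days, 84-167 days" and 168 days or more. Two rules govern them:

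- Denominator: "Denominators for exposure intervals will be based on the number of subjects who were exposed as of the first day of the interval".
- Treatment-emergent events that start after the last dose: "the exposure interval for the event will be considered the interval of the last day of exposure to study medication".

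One AE is treated differently: "A Kaplan-Meier plot of the time to the first onset of treatment emergent insomnia (combined term"), with a daily prevalence among subjects still in the treatment period. SAP 7.1.2 adds a Kaplan-Meier plot of time to early discontinuation. SAP 7.1.4 tabulates treatment duration with finer late cut points, including 196, 252 and 308 days.

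**The concern.** A table of AEs by time on drug is read to see whether risk changes with longer exposure. Here each column is the percentage of entering subjects who have an event in the interval, and the last interval is about 15 times as long as the first. A reader comparing columns sees interval length mixed with risk, and a steady risk looks like an increasing one. Everything from Week 24 to Week 52 falls in one column, so the table cannot separate an event near Day 170 from one near Day 350.

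The overall percentages have a different weakness. A subject who leaves early has less time to report an event but counts fully in the denominator, so the crude figure drops as dropout rises. If the former-placebo and former-dasotraline groups, tabulated side by side, drop out at different rates, their crude percentages can differ even when their event rates are the same.

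**Working it through.** **Inputs from the documents.** Interval limits and the denominator rule: SAP 7.4.2. Planned last treatment day, 364: Protocol Table 2. The plan states no AE rate, event count or dropout rate, so there is no figure of its own to reproduce.

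**Assumptions.** Constant hazard h of 0.1 to 1.0 per year; independent exponential dropout of 0% to 60% over one year. A year is 365.25 days.

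**Step 1, interval widths** (last day − first day + 1, last interval closed at Day 364): 13, 14, 56, 84 and 364 − 168 + 1 = 197 days, total 364. The last is 197/13 = 15.2 times the first and holds 197/364 = 54% of planned treatment.

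**Step 2, interval length alone, no dropout.** Treating every subject who enters an interval as event-free, the percentage is 1 − exp(−h·d/365.25) for width d.

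| h per year | 1-13 | 14-27 | 28-83 | 84-167 | 168 or more | last/first |
|---|---|---|---|---|---|---|
| 0.1 | 0.36% | 0.38% | 1.5% | 2.3% | 5.2% | 14.8 |
| 0.2 | 0.7% | 0.8% | 3.0% | 4.5% | 10.2% | 14.4 |
| 0.5 | 1.8% | 1.9% | 7.4% | 10.9% | 23.6% | 13.4 |
| 1.0 | 3.5% | 3.8% | 14.2% | 20.6% | 41.7% | 11.9 |

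Risk is the same in every column of a row.

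**Step 3, dropout within an interval.** With dropout hazard m = −ln(1 − dropout) per year, the percentage is h/(h+m) × [1 − exp(−(h+m)·d/365.25)]. At h = 0.2 the last interval shows 9.3% with 30% dropout and 8.1% with 60%, instead of 10.2%. The last/first ratio becomes 13.2 and 11.6.

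**Step 4, first onsets only.** The denominator is all subjects exposed at interval entry, including those who already had the event. If a subject counts only at first onset, the last-interval percentage is multiplied by exp(−h·167/365.25), the chance of no event in the first 167 days. At h = 1.0 without dropout it is 0.633 × 41.7% = 26.4%, a ratio of 7.5; with 60% dropout the ratio is 6.2.

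**Step 5, overall crude incidence over one year.** Crude = h/(h+m) × [1 − exp(−(h+m))], with h = 0.2.

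- Full follow-up: 1 − exp(−0.2) = 18.1%.
- 30% dropout, m = 0.357: 0.2/0.557 × (1 − exp(−0.557)) = 15.3%.
- 60% dropout, m = 0.916: 0.2/1.116 × (1 − exp(−1.116)) = 12.0%.

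The crude figure is thus 15% to 34% lower in relative terms.

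**Step 6, person-time.** Expected time at risk in an interval is [1 − exp(−(h+m)·d/365.25)]/(h+m) years per subject entering event-free. Dividing the Step 3 percentage by this leaves h: 20 per 100 person-years in every interval, at every dropout level.

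**The case against.** The study is an uncontrolled, descriptive extension with no hypotheses. The SAP's measure is the one in Protocol 15.3.3.1, the interval limits are labelled, and the by-exposure tables are supplementary. All of that stands: nothing here is an internal error or a contradiction.

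A reader might infer three stronger things that the documents do not support.

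- *Late-onset events cannot be located.* SAP 7.4.2 provides listings of deaths, SAEs, AESIs, discontinuations due to AEs and all AEs. Insomnia has its onset curve and daily prevalence. Laboratory, vital-sign and ECG abnormalities are tabulated by visit. Only the by-exposure summary table lacks timing after Day 168.
- *The by-exposure tables ignore dropout.* They do not: denominators reset at each interval, so earlier dropout is handled. Only dropout within an interval is left, mainly in the 197-day one. The fuller objection applies to overall incidence, and there the discontinuation curve and the duration table let a reader see the follow-up behind the percentages.
- *A 14-fold artefact is to be expected.* That figure needs zero dropout and event-free entry, and Steps 3 and 4 give smaller ratios. Constant hazard and independent dropout are also assumptions. Protocol 4.3 reports discontinuation due to AEs of 11.2% and 29.7% at 4 and 8 mg/day in the adult ADHD study, but that is another population and one reason for leaving only.

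A rate per 100 person-years has limits too: long event-free follow-up dilutes early-onset events. It supplements the percentages; it does not replace them.

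**Conclusion.** The concern holds as a weakness of presentation in tables that serve the primary objective. Apart from insomnia, the plan has no AE summary that accounts for time at risk. Under a constant hazard the by-exposure percentages rise about 12- to 15-fold through interval length alone (hazards of 1.0 to 0.1 per year, no dropout, event-free entry). The rise falls to about 6-fold at 1.0 per year with 60% dropout and first onsets only. At 0.2 per year, overall crude incidence is 15.3% to 12.0% with 30% to 60% dropout, against 18.1% with full follow-up. The interval widths come from the documents; the hazards and dropout rates are assumed. The direction of both effects is the same across the ranges shown, but the size is not known for this trial. A cheap improvement is warranted.

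**What to change.** In SAP 7.4.2, for overall AEs, SAEs, AEs leading to discontinuation and AESIs:

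1. Add the number of subjects with a first event per 100 person-years, overall and per exposure interval. Person-time runs to the first event or the end of the treatment-emergent window (7 days after discontinuation, 14 for SAEs and deaths). Window time after the last dose goes to the interval that receives post-dose events under the existing rule, so that numerator and denominator match.
2. Split the last interval into 168-251 days and 252 days or more; 252 is already a cut point in SAP 7.1.4. Do not add a separate onset interval from Day 364. That category identifies completers in a duration table, but as an onset interval it would hold only one or two days of planned treatment and would collect completers' post-dose events.
3. Keep the crude n (%) tables.

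The split alone is not enough. The new widths are 84 and 113 days, and at 0.2 per year the percentages would still be 4.5% and 6.0% against 0.7% in the first interval.

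The cost is a few more columns from dose and onset dates already collected, with sparser counts in the late intervals. A single overall rate describes risk well only if the hazard is roughly constant, so it should be read alongside the per-interval rates.
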